7.1.2 Serious Adverse Events

A serious adverse event (SAE) is any experience that suggests a significant hazard, contraindication, side effect, or precaution. It is any AE that results in any of the following outcomes:

- Death
- A life-threatening adverse event
- In-patient hospitalization or prolongation of existing hospitalization
- A persistent or significant disability or incapacity
- A congenital anomaly/birth defect in the offspring of a subject who received the study treatment
- Important medical events that may not be immediately life-threatening or result in death or hospitalization but which may jeopardize the subject or may

A Pilot Study to Investigate the Effects of Humic Acid on Flu Symptoms

Protocol 10HFHL

require intervention to prevent one of the outcomes listed above. Examples of such events are intensive treatment in an emergency room or at home for allergic bronchospasm; blood dyscrasias or convulsions that do not result in hospitalization; or the development of drug dependency or drug abuse

7.1.3 Unexpected Adverse Reaction

An unexpected adverse reaction is an adverse reaction, the nature and severity of which is not consistent with the applicable product information (e.g., Investigator's Brochure for an unapproved investigational product or package insert/summary of product characteristics for an approved product).

7.1.4 Laboratory Test Abnormalities

Any treatment-emergent abnormal laboratory result which is clinically significant, i.e., meeting one or more of the following conditions, should be recorded as a single diagnosis on the AE form in the study record:

- Accompanied by clinical symptoms
- Leading to interruption or discontinuation of the investigational product
- Requiring a change in concomitant therapy

This applies to any protocol- and non-protocol-specified laboratory result from tests performed after the first dose of investigational product that falls outside the laboratory reference range and meets the clinical significance criteria (i.e. AST and/or ALT > 2 x ULN).

This does not apply to any abnormal laboratory result which falls outside the laboratory reference range but which does not meet the clinical significance criteria or those which are a result of an AE which has already been reported.

Any laboratory result abnormality fulfilling the criteria for a serious adverse event (SAE) should be reported as such, in addition to being reported as an AE in the study record.

7.2 Treatment and Follow-up of AEs and Laboratory Abnormalities

7.2.1 Treatment and Follow-up of AEs

AEs, especially those for which the relationship to investigational product is suspected, should be followed up until they have returned to baseline status or stabilized.

If after follow-up a return to baseline status or stabilization cannot be established, an explanation should be recorded in the study record.

7.2.2 Follow-up of Laboratory Abnormalities

In the event of clinically significant unexplained abnormal laboratory test values, the tests should be repeated and followed up until they have returned to the normal range and/or an adequate explanation of the abnormality is found. If a clear explanation is established it should be recorded in the study record.

7.3 Reporting of SAEs and Unexpected Adverse Reactions

Notification of any serious adverse events must be made in writing to the study sponsor within 24 hours of learning of the event. The IRB will be notified of all SAEs and unexpected adverse reactions.

A Pilot Study to Investigate the Effects of Humic Acid on Flu Symptoms

Protocol 10HFHL

8. STATISTICAL EVALUATION

8.1 Determination of sample size

Forty subjects will be randomized in an equal ratio to one of the two treatments. As this is a pilot study a formal sample size calculation was not performed.

8.2 Analysis Plan

The distribution of baseline characteristics in the two groups will be compared descriptively. Efficacy analysis will include all subjects completing at least one follow-up visit post randomization. For analysis of symptom scores, there will be no imputation of missing data. The average score will be based on the available number of days of data. Treatment group comparisons for primary and secondary outcomes will be made using the ANOVA (analysis of variance) model. Safety analysis will include all subjects randomized to treatment. Safety analysis will include parameters of haematology, general chemistry, and adverse events. Compliance with investigational product usage and the usage of concomitant medications will be compared between groups using Chi-square.

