2. STUDY OBJECTIVES

The primary objective of this study is to assess the efficacy of humic acid on flu symptoms as assessed by the alleviation of symptoms after 7 and 14 days of treatment in adults with influenza A or B. This will be determined by the use of a daily diary to assess the following symptoms during the trial on a 4-point scale (0=absent, 1=mild, 2=moderate, 3=severe):

[figure not shown]
- cough
- fever
- runny nose
- stuffy nose
- aches and pains
- headache
- chills
- sneezing
- ear aches
- fatigue

Additional endpoints will include:

- Visual analog scale (VAS) 0-100 mm, for ability to perform usual activities
- Doses of concomitant therapies for symptom treatment
- Immunological markers (WBC differential, CD4+, CD8+, TNF α , IL-8)

A Pilot Study to Investigate the Effects of Humic Acid on Flu Symptoms
Protocol 10HFHL

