Subjects will be allowed to use concomitant therapies for the treatment of symptoms (i.e., antipyretics, expectorants, throat lozenges). Subjects will be asked to refrain from taking acetaminophen, aspirin, ibuprofen or NSAID within 4 hours prior to temperature readings.

The next visit will be scheduled for day 7 (± 2 days).

Subjects will return to the clinic for follow-up at days 7 and 14.

6.2 Visit 2 / Day 7

Subjects will return the clinic on day 7 (± 2 days). Any remaining investigational product and packaging, and diary will be returned and a new supply of product and new diary will be dispensed.

Study visit assessments will include:

- review of subject diary, concomitant therapies and adverse events
- compliance calculation
- vitals signs
- self-administered VAS questionnaire
- laboratory tests (hematology and immunological markers)

The next visit will be scheduled for day 14 (± 2 days).

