6.3 Visit 3 / Day 14 – End of Study

Subjects will return to the clinic on day 14 (± 2 days). Any remaining investigational product and packaging, and diary will be returned.

Study visit assessments will include:

- review of subject diary, concomitant therapies and adverse events
- compliance calculation
- vitals signs
- self-administered VAS questionnaire
- laboratory tests (hematology, chemistry and immunological markers)

A Pilot Study to Investigate the Effects of Humic Acid on Flu Symptoms

Protocol 10HFHL

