Appendix 3. Daily Symptoms Scores

Subjects will be asked to rate how severe their flu symptoms are by means of a self-administered questionnaire to be completed daily. Each response will be based on a 4-point scale:

- 0 = *absent*
1 = *mild*
2 = *moderate*
3 = *severe*

Symptoms

1. *Cough*
2. *Fever*
3. *Runny nose*
4. *Stuffy nose*
5. *Aches and pains*
6. *Headache*
7. *Chills*
8. *Sneezing*
9. *Ear aches*
10. *Fatigue*

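### Averaging symptom scores over whichever diary days exist compares subjects on different parts of a declining illness, and biases the primary comparison when early loss differs by arm or diaries stop on recovery

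*Protocol*

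**What the plan says.** The primary objective (Section 2) is "alleviation of symptoms after 7 and 14 days of treatment in adults with influenza A or B", measured by a daily diary. Appendix 3 lists ten symptoms, and "Each response will be based on a 4-point scale" from 0 to 3.

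Section 8.2 fixes four things about the analysis:

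- Missing days: "For analysis of symptom scores, there will be no imputation of missing data".
- Summary per subject: "The average score will be based on the available number of days of data".
- Analysis set: "Efficacy analysis will include all subjects completing at least one follow-up visit post randomization".
- Test: "Treatment group comparisons for primary and secondary outcomes will be made using the ANOVA (analysis of variance) model".

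Diaries are handed in at the visits. Under Section 6.2, "Subjects will return the clinic on day 7 (± 2 days"), and a fresh diary is then issued. Under Section 6.3, "Subjects will return to the clinic on day 14 (± 2 days"). The protocol states no minimum number of diary days, no common averaging window and no adjustment for the days observed.

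**The concern.** The protocol itself notes in Section 1 that most people recover from influenza. Scores are therefore expected to be high early and low late, and a mean over available days reflects which days were recorded as well as how ill the subject was.

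Two patterns matter:

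- **Loss after Visit 2.** A subject who leaves after Visit 2 has returned one diary, covering roughly the first 5 to 9 days. One follow-up visit is enough for the efficacy set, so an average of the worst days is compared directly with 14-day averages. If this happens more often in one arm, that arm looks worse for no clinical reason.
- **Stopping on recovery.** A subject who stops recording once well loses the low scores. The faster the recovery, the more low scores are lost, so a treatment that speeds recovery loses part of its visible benefit even if recording habits are the same in both arms.

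At stake is the primary efficacy comparison: a false difference in the first case, a missed effect in the second.

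**Working it through.** **Inputs from the protocol.** 40 subjects, 1:1, so 20 per arm (Section 8.1); 14 days of treatment (Section 3); Visit 2 on Day 5-9 and Visit 3 on Day 12-16 (Sections 6.2 and 6.3); ten items scored 0-3 (Appendix 3). The protocol gives no effect size, SD, significance level, dropout rate or missing-day rate, so it has no figure to reproduce.

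**Assumptions.** Items summed to a total of 0-30; total score 15 at Day 0 (SD 4 between subjects); exponential decline with a 4-day time constant (log-scale SD 0.3); daily noise SD 1; two-sided 5% test. Simulations use 4000 runs.

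**Step 1: one illness, different averages.** With q = exp(-1/4) = 0.7788, the mean over Days 1 to k is (15/k) × q(1 - q^k)/(1 - q), where q/(1 - q) = 3.521.

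- k = 5: 3.000 × 3.521 × 0.7135 = 7.5
- k = 7: 2.143 × 3.521 × 0.8262 = 6.2
- k = 9: 1.667 × 3.521 × 0.8946 = 5.3 (5.25 before rounding)
- k = 14: 1.071 × 3.521 × 0.9698 = 3.7

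The pattern does not depend on this curve. A linear fall from 20 to 0 by Day 10 gives 13.33 over Days 1-7 and 7.14 over Days 1-14. A slow fall from 20 to 4 gives 16.31 and 12.00. Only a flat course is unaffected.

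**Step 2: early loss that differs by arm, no true effect.** The means for k = 5, 6, 7, 8, 9 are 7.54, 6.84, 6.23, 5.71 and 5.25, which average 6.31. The excess over the 14-day mean is 6.31 - 3.66 = 2.65. Expected bias = excess × difference in loss:

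- 25% v 5%: 2.65 × 0.20 = 0.53. Simulation: about +0.5 points, 12% false positives.
- 10% v 5%: 2.65 × 0.05 = 0.13. Simulation: +0.13 points, about 5% false positives.

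A different assumed course (score 20, half-life 3 days) has a larger gap: 11.10 - 6.65 = 4.45. Loss after Day 7 of 30% v 10% then gives 4.45 × 0.20 = 0.89 expected; simulation gave 0.86 and 20% false positives.

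**Step 3: stopping on recovery, with a true effect.** For a linear fall from 20 to 0 on Day r, the mean up to Day r is (20 + 0)/2 = 10 whatever r is, while the 14-day mean is 10r/14. Recovery on Day 7 v Day 10 gives true means of 5.00 v 7.14, yet both diaries average 10.0 if they end on recovery: a benefit of 2.14 points disappears.

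Under the exponential course with a time constant of 3 v 4 days:

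| Subjects stopping when well | Estimate | Power |
|---|---|---|
| None | -0.91 | 56% |
| 25% | -0.78 | 36% |
| 80% | -0.53 | 21% |

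The score at which a subject counts as well is a further assumption, and a different cut-off moves these figures.

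**Step 4: patterns that do not bias.**

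- Equal loss after Day 7 (20% in both arms, half-life course, no effect): difference 0.00, type I error 0.047. The SD of the estimate rises from 0.44 to 0.76, and power for a 20% shorter half-life falls from 0.65 to 0.29.
- Days missing purely at random, 10% v 30%, no effect: difference 0.005, type I error 0.048.
- Every diary ending at random on Days 12-16, otherwise complete: bias 0.00, false positives about 5%.

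**The case against.** Several points on the other side stand.

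- **Bias is conditional.** A reader might infer that any missing diary day biases the comparison. Step 4 shows otherwise: equal loss with no effect costs only precision, and purely random gaps do not bias.
- **Very early dropout is mostly outside the efficacy set.** Diaries ending on Days 3-5 in 25% v 5% of subjects would give about +0.91 points and 21% false positives, and a reader might take that as the size of the problem. Entry to the set needs a follow-up visit, and Visit 2 falls on Day 5 at the earliest. Without diaries that end before Day 5, the figures drop to +0.32 and 7.5%. Some such subjects could still enter, through the withdrawal evaluation in Section 4.4 or by attending with an abandoned diary, but this is not the main case.
- **The visit window is essentially harmless.** A reader might infer that the ±2 days alone distort the average. They do not: a new diary is issued at Visit 2, so no days are lost there, and variation at Visit 3 gave no bias.
- **Diary habits may be good.** The same diary carries temperature, product use, other therapies and adverse effects, and is reviewed at both visits. This makes stopping on recovery less likely but does not exclude it. The 25% to 80% range is an assumption.
- **It is a pilot, and a separate SAP may exist.** Pilot status lowers the stakes. But the study is called an efficacy pilot and tests between arms, and the averaging rule stands in the protocol, so it is not a detail left open for an SAP.

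**Conclusion.** The concern holds in conditional form. The rule in Section 8.2 gives identical illnesses different averages whenever scores decline. It biases the comparison when early loss differs between arms, and it shrinks a real effect when subjects stop the diary on recovery.

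Under the assumed course with 20 per arm, plausible cases run from negligible (10% v 5% loss: 0.13 points, about 5% false positives) to material (25% v 5%: about 0.5 points, 12%). With a true effect, power falls from 56% to between 36% and 21%. These sizes rest on the assumed curve, SDs, missing-day rates and 5% level. The protocol states none of them, so the actual size is unknown. The documents do not support saying that the result will be biased, only that the rule gives no protection in the two patterns a self-limiting illness makes likely. This should be fixed, but it does not invalidate the design.

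**What to change.** Replace the averaging sentence in Section 8.2 so that the arms are compared on the same fixed treatment days:

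- Assign each diary entry to a treatment day, and exclude entries after Day 14.
- Analyse the daily total score in a repeated-measures mixed model with arm, day, arm-by-day and baseline score.
- Name a parsimonious covariance structure, for example first-order autoregressive plus a subject effect. An unstructured matrix for 14 days has 14 × 15/2 = 105 parameters, too many for 40 subjects.
- Take the treatment effect as the mean of the day-specific differences over Days 1-7 and over Days 1-14.
- Keep the available-days mean as a sensitivity analysis, and report the number of diary days by arm beside it.

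A small simulation of a mixed model with day included gave an estimate of -0.93 and 49% power when 80% of subjects stop when well, against -0.53 and 21% for the available-days mean. With only 150 runs (standard error about 4 percentage points on the power), and without testing this particular covariance structure, that is indicative only.

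The cost is a rewording and a slightly more complex model. It needs no more subjects, visits or data, because daily scores are already collected. The model assumes that missing days depend only on scores already observed; if subjects stop for reasons their recorded scores do not show, some bias remains.

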3. STUDY DESIGN

This is a multi-center, randomized, double-blind, placebo-controlled, parallel-group efficacy pilot study.

The study will consist of a single 14-day treatment period. Screening and randomization will occur on the same day.

The planned sample size for the study is 40 subjects, with 20 subjects randomized equally to each of the two study arms. The subjects will be recruited over the flu season.

Subjects will be randomized to one of the two treatment groups: Humic Acid or Placebo.

In order to evaluate primary and secondary endpoints, study assessments will be conducted at baseline, Day 7 and Day 14.

The study will be conducted at two sites in the US.

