5.2 Labeling and Coding

The humic acid and placebo investigational products will be labeled according to the requirements of ICH-GCP guidelines as well as applicable local regulatory guidelines. Investigational products will be randomized and coded by the sponsor. Each investigator will be provided with a randomization list indicating the order of randomization. Each subject will be assigned a randomization code according to the order of the randomization list. The investigator will be provided with sealed envelopes for each randomization code. These envelopes are to remain sealed except in the event of an emergency. In the event that it is necessary to unblind a subject's treatment, the envelope labeled with the subject's randomization code will be opened. Notification of unblinding must be reported to the study sponsor within 24 hours.

Sample Label

Randomization Code: *****	Protocol No.: 10HFHL
Humic Acid Lot No. 072604 or Placebo	
Expiry date: December 2016	
Investigational Natural Health Product	
To be used under the supervision of a qualified investigator.	
Sponsor & Manufacturer:	Laub Biochemicals Corporation
	[name]
For investigational use only. Keep out of reach of children. Store at room temperature.	
Contains: 60 tablets	
Investigator Name: _____	Phone: _____
Subject No.: _____	Subject Initials: _____
Date dispensed: _____	Date returned: _____

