6.1 Visit 1 – Screen / Baseline

At screening, a Subject Information and Consent Form will be given to each potential subject. The subject will read the information carefully and will be given the opportunity to seek more information if needed. The subject will also be provided with the option of taking the consent form home to review prior to making his or her decision. If agreeable, the subject will sign the consent form and receive a duplicate. Once consent has been obtained, the screening visit will proceed. Each subject will be assigned a screening number at the screening visit. After the subject has signed the informed consent, the screening number will be assigned sequentially and entered in the Screening and Enrollment Log. Screening numbers will be allocated in the chronological order of the subject's signing the informed consent.

Visit 1 shall include:

- review of medical history and concomitant therapies
- vitals signs (heart rate, blood pressure, temperature)
- physical examination (excluding breast, rectal/vaginal examination)
- self-administered questionnaires (symptoms and VAS)
- urine pregnancy test for women of childbearing potential
- a review of inclusion/exclusion criteria
- laboratory tests (hematology, chemistry, and immunological markers)

Eligible subjects will be randomized to humic acid or placebo via the Randomization Schedule provided to the Investigator on the same day.

Subject randomization numbers are to be allocated in the order listed on the Randomization Schedule.

After all visit assessments are performed, subjects will be dispensed the study product.

A Pilot Study to Investigate the Effects of Humic Acid on Flu Symptoms

Protocol 10HFHL

Subjects will receive one of the following treatment regimens:

- humic acid as 2 tablets TID for a total of 6 tablets daily for 14 days
- placebo as 2 tablets TID for a total of 6 tablets daily for 14 days

Subjects will be instructed in detail by site personnel about the dosing regimen. The first dose of study product is to be taken the day after Visit 1 (treatment day 1).

Paper diaries and electronic thermometers will be provided to the subjects. Diaries will be used by subjects to record daily symptom scores, daily oral temperature, investigational product use, concomitant therapy use including treatments taken for symptoms, and changes in health status including adverse effects.

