Appendix 2. Flu Symptoms Questionnaire

Subjects will be asked to indicate by means of interview all symptoms present at screening in order to assess eligibility. Investigator or designate will record the presence of the following symptoms:

Respiratory symptoms

1. *Cough*
2. *Sore throat*
3. *Nasal symptoms*
4. *Sneezing*

Fever

5. ≥ 38.0 °C (≥ 100.4 °F) taken orally
6. *Subject report of fever within the past 24 hours*

Constitutional symptoms

7. *Headache*
8. *Myalgia (muscle pain)*
9. *Sweats/chills*
10. *Fatigue*

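### Section 8.2 compares the arms by ANOVA with no baseline term, although pre-dose values of the outcomes are collected: valid, but probably less precise than it could be

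*Protocol*

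**What the plan says.** Section 8.2 fixes the method in one sentence: "Treatment group comparisons for primary and secondary outcomes will be made using the ANOVA (analysis of variance) model". It names no covariate, site factor or change score. Its only stated use of baseline is descriptive: "The distribution of baseline characteristics in the two groups will be compared descriptively". For symptoms the outcome is a mean over diary days: "The average score will be based on the available number of days of data".

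On design, Section 3 says: "The planned sample size for the study is 40 subjects, with 20 subjects randomized equally to each of the two study arms". There are two sites. Section 8.1 sets no precision target: "As this is a pilot study a formal sample size calculation was not performed".

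Pre-dose values are available. Section 6.1 and Appendix 1 place the VAS, hematology (including WBC differential and T lymphocyte counts) and the cytokines at Visit 1 and again at both later visits. Sections 5.5 and 6.1 put the first dose on the day after Visit 1. Appendix 1 also marks the daily symptom scores at Visit 1 (Day 0), in a row separate from the symptoms questionnaire. That questionnaire is described in Appendix 2: "Subjects will be asked to indicate by means of interview all symptoms present at screening in order to assess eligibility". It records presence only; the 0-3 severity scale is in Appendix 3.

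On allocation, Section 5.2 says: "Each investigator will be provided with a randomization list indicating the order of randomization". Neither there nor elsewhere does the protocol say that allocation is stratified or blocked by site.

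**The concern.** The primary objective in Section 2 is the alleviation of symptoms, which implies a starting level. Section 4.1 admits subjects on a respiratory symptom plus fever or one constitutional symptom, with no minimum severity score, so starting levels can vary. In a trial of 40 the arms can differ at entry by chance, and an unadjusted comparison carries part of that difference into the estimate. The values needed to remove it are already collected. What is at stake is precision in a small pilot.

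**Working it through.** The protocol gives no alpha, power, SD or effect size, so there is no planned figure to reproduce.

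**Inputs from the protocol:** 20 subjects per arm; two arms; ANOVA without a baseline term.

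**Assumptions, not in the protocol:** two-sided alpha 0.05; 80% power; all 40 subjects analysed; baseline-outcome correlation r from 0 to 0.7.

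**Chance imbalance at baseline (in SD units)**
- Standard error of the difference in means: sqrt(2/20) = 0.316.
- P(|difference| > 0.5) = 2 × [1 − Φ(0.5/0.316)] = 2 × [1 − Φ(1.58)] = 0.114.
- P(|difference| > 0.3) = 2 × [1 − Φ(0.3/0.316)] = 0.343.
- Expected shift of the unadjusted treatment difference, given a 0.5 SD imbalance: r × 0.5.

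**Detectable difference with ANOVA**
- Normal approximation: (1.960 + 0.842) × 0.316 = 0.886 SD.
- Noncentral t, 38 df: 0.909 SD.

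**Detectable difference with ANCOVA on baseline**
- Variance factor relative to ANOVA: (1 − r²) × (1 + 1/36). The second term is the price of estimating one covariate with N = 40.
- Noncentral t, 37 df. Equivalent ANOVA size per arm = 20 / factor.

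| r | Variance factor | Detectable difference (SD) | Equivalent n per arm | Power for 0.8 SD | Shift from 0.5 SD imbalance (SD) |
|---|---|---|---|---|---|
| ANOVA | 1 | 0.91 | 20 | 69.3% | r × 0.5 |
| 0 | 1.028 | 0.92 | 19.5 | 68.1% | 0 |
| 0.2 | 0.987 | 0.90 | 20.3 | 69.9% | 0.10 |
| 0.3 | 0.935 | 0.88 | 21.4 | 72.2% | 0.15 |
| 0.5 | 0.771 | 0.80 | 25.9 | 80.1% | 0.25 |
| 0.7 | 0.524 | 0.66 | 38.2 | 92.5% | 0.35 |

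Break-even, ignoring the single lost degree of freedom: (1 − r²) × 37/36 = 1 gives r² = 1/37, so r is about 0.16. Below that, adjustment loses slightly; above it, adjustment gains.

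**Site, only if arms are balanced within site.** For assumed site shares of outcome variance of 5%, 10% and 20%, leaving site out makes the nominal 5% test run at about 4.5%, 4.0% and 3.0%. Including site gives detectable differences of 0.89, 0.86 and 0.81 SD. With no site effect the figure stays at 0.91 SD.

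**The case against.** **The analysis is valid as written.** A reader might infer that an unadjusted ANOVA gives a biased or invalid result at 20 per arm. It does not. Under randomisation it is unbiased, and its standard error already reflects the shift that a chance imbalance causes. This stands in full.

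**The gain is not guaranteed.** A reader might infer that adjustment narrows every interval at no cost. At r of 0.2 or below the gain is about nil, and at r = 0 there is a small loss. The protocol gives no correlation. In a self-limiting illness scored at Days 7 and 14, many late scores may be near zero and r may be low. This also stands, and it is why the result is shown as a range.

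**The SAP may say more.** The word ANOVA does not exclude a site factor or an analysis of change from baseline. That is fair for site. It does not rescue the baseline point: if variances are equal at both times, a change score has variance factor 2(1 − r), which is 1.6, 1.0 and 0.6 at r = 0.2, 0.5 and 0.7, against 0.987, 0.771 and 0.524 for ANCOVA. The protocol names a model for all these outcomes, so it has made a choice rather than left one open.

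**Site.** A reader might infer that each site was randomised separately and that site must therefore be in the model. Section 5.2 says only that each investigator receives a list. Separate lists are plausible, but balance within site is not stated, so the site term can only be conditional.

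**Symptom baseline.** A reader might infer that no pre-dose severity score exists, because Section 6.1 calls the Visit 1 symptom questionnaire self-administered while Appendix 2 is an interview on presence. But Appendix 1 marks the daily scores at Day 0, and Appendix 3 is itself self-administered. A pre-dose rating therefore appears to be scheduled. What remains is that no section names it as the baseline.

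**Conclusion.** The point holds as a matter of efficiency. Section 8.2 commits the primary and secondary comparisons to a model with no baseline term, while same-measure pre-dose values exist for the VAS and all the immunological markers, and apparently for the symptom score. The case is firmest for the VAS and the markers. For symptoms it rests on the Day 0 mark in Appendix 1.

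The size depends on correlations that the protocol does not supply. From 0.91 SD, the detectable difference moves to between 0.90 SD (r = 0.2) and 0.66 SD (r = 0.7), with a loss of about 0.01 SD at r = 0. The improvement becomes material at about r = 0.5, where it is worth about six further subjects per arm (25.9 against 20). No figure stated in the protocol changes.

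**What to change.** - In Section 8.2, replace ANOVA with ANCOVA: treatment as the factor and the Day 0 value of the same measure as covariate, for each outcome that has one.
- State that the symptom baseline is the Day 0 rating on the 0-3 scale of Appendix 3, completed before the first dose. Say so in Section 6.1 as well, and keep that rating out of the post-dose average. The Appendix 2 interview cannot serve, because it records presence only.
- In Section 5.2, state whether the investigator-held lists are balanced within site. Include site in the model only if they are.

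The cost is one degree of freedom for baseline and one more for site if it is included, out of 38, plus the loss of about 0.01 SD if baseline proves uninformative. No new visit, sample or form is needed, since the Day 0 rating is already marked in Appendix 1.

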7.1 Adverse Events and Laboratory Abnormalities

7.1.1 Adverse Events

An adverse event (AE) is any untoward medical occurrence in a clinical investigation subject who has been administered an investigational product and which does not necessarily have a causal relationship with this treatment. An AE can be any unfavorable and unintended sign (including an abnormal laboratory finding), symptom, or disease temporally associated with the

A Pilot Study to Investigate the Effects of Humic Acid on Flu Symptoms

Protocol 10HFHL

use of a product, whether or not it is considered related to that product. Pre-existing conditions which worsen during a study are to be reported as AEs. Flu symptoms are recorded daily by the subject and may worsen during the trial. These events will be captured as daily symptom scores and are not to be recorded as separated adverse events.

During the study, subjects should record any adverse effects in their diary. At each visit the subject will be asked "Have you experienced any difficulties or problems since I saw you last"? Any (AEs) will be documented in the study record and will be classified according to the description, duration, intensity, frequency, and outcome. The investigator will assess any AEs and decide causality.

Intensity of AEs will be graded on a three-point scale (mild, moderate, severe) and reported in detail in the study record:

Mild:	Awareness of event but easily tolerated
Moderate:	Discomfort enough to cause some interference with usual activity
Severe:	Inability to carry out usual activity

The causality relationship of investigational product to the adverse event will be assessed by the investigator as either:

Most probable:	There is a reasonable relationship between the investigational product and AE. The event responds to withdrawal of investigational product (dechallenge) and recurs with rechallenge when clinically feasible.
Probable:	There is a reasonable relationship between the investigational product and AE. The event responds to dechallenge.
Possible:	There is a reasonable relationship between the investigational product and AE. Dechallenge information is lacking or unclear.
Unlikely:	There is a temporal relationship to investigational product administration but there is no reasonable causal relationship between the investigational product and the AE.

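### The safety analysis set counts every randomized subject, while an adverse event can by definition occur only in a dosed subject, so any never-dosed subject dilutes that arm's adverse event proportion

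*Protocol*

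**What the plan says.** Section 8.2 of the protocol fixes the safety set without any dosing condition: "Safety analysis will include all subjects randomized to treatment". It then gives the content: "Safety analysis will include parameters of haematology, general chemistry, and adverse events". Section 8.2.3 adds that AEs are tabulated by body system and treatment, without naming another denominator.

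The events are defined by exposure. Section 7.1.1: "An adverse event (AE) is any untoward medical occurrence in a clinical investigation subject who has been administered an investigational product". Section 7.1.4 applies the same limit to laboratory abnormalities reportable as AEs, which must come from "tests performed after the first dose of investigational product".

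On timing, section 3 says: "Screening and randomization will occur on the same day". Section 6.1 says: "After all visit assessments are performed, subjects will be dispensed the study product". Sections 5.5 and 6.1 both place the first dose on the day after the randomization visit. Section 6.2 and Appendix 1 schedule the next visit at Day 7 ± 2. Sections 4.4 and 8.2.2 state that subjects who leave are not replaced.

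**The concern.** The numerator of an AE proportion requires exposure and the denominator does not. A subject who is randomized, goes home with the product and never takes a tablet cannot contribute an AE under section 7.1.1, but section 8.2 still counts that subject as having been observed without one.

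The design leaves room for this. At least one day separates randomization from the first dose, and no visit is scheduled in between. Section 4.4 lets a subject withdraw at any time for any reason, and also provides for discontinuing subjects found to have been wrongly enrolled. Either could happen before Treatment Day 1.

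What is at stake is how the AE table reads. Section 1 describes the trial as the first test of humic acid on flu symptoms in humans, so readers will take the AE percentages as rates in people who took the product. With 20 subjects per arm, one non-starter is 5% of the denominator.

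**Working it through.** The protocol gives no AE rate, no expected number of non-starters and no sample size calculation, so it has no figure of its own to reproduce beyond 40 / 2 = 20 per arm (sections 3 and 8.1), which is consistent. The values of k, p and q below are assumptions.

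**Step 1: can a randomized subject be never dosed and still be in the set?**

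| Element | Rule | Section |
|---|---|---|
| Randomization | Day 0, same day as screening | 3, 6.1 |
| Dispensing | End of Visit 1, Day 0 | 6.1 |
| First dose | The following day | 5.5, 6.1 |
| Next visit | Day 7 ± 2 | 6.2, Appendix 1 |
| Event counts as an AE | Only if product was administered | 7.1.1 |
| Laboratory abnormality counts as an AE | Only after first dose | 7.1.4 |
| Subject is in the safety analysis | If randomized | 8.2 |

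Yes. No other section limits the set to dosed subjects. That the first dose is taken unsupervised, presumably at home, is inferred from this schedule; the protocol does not say it.

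**Step 2: dilution within one arm.** Let p be the AE proportion among dosed subjects and k the number never dosed in an arm of 20. Only 20 − k subjects can contribute events, so

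reported proportion = p × (20 − k) / 20.

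| k (assumed) | Relative change | p = 20% (assumed) | p = 30% (assumed) |
|---|---|---|---|
| 0 | 0 | 20% | 30% |
| 1 | −5% | 19% | 28.5% |
| 2 | −10% | 18% | 27% |
| 3 | −15% | 17% | 25.5% |

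**Step 3: the same effect with a fixed count.** Four subjects with an AE give 4/20 = 20.0% on all randomized subjects. On dosed subjects they give 4/19 = 21.1% (k = 1), 4/18 = 22.2% (k = 2) and 4/17 = 23.5% (k = 3).

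**Step 4: between-arm difference.** Take p = 20% in both arms, so the true difference is zero.

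- 3 non-starters on humic acid, 0 on placebo: 17% − 20% = −3 points, and humic acid looks safer than it is.
- 0 on humic acid, 3 on placebo: 20% − 17% = +3 points, and humic acid looks less safe than it is.
- Equal numbers in each arm: both proportions fall and the difference stays at zero.

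**Step 5: how likely is at least one non-starter?** If each of the 40 subjects independently has probability q of never dosing, the chance of at least one is 1 − (1 − q)^40.

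| q (assumed) | Chance of at least one | Expected number, 40q |
|---|---|---|
| 1% | 33% | 0.4 |
| 2% | 55% | 0.8 |
| 5% | 87% | 2 |
| 10% | 99% | 4 |

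A single non-starter is plausible at modest q. Several in one arm would need a higher q, for which the protocol offers no evidence.

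**The case against.** **The effect may be nil, and is small in any case.** If every subject takes one tablet, the two sets are identical. Subjects are ill, have agreed to take the product (section 4.1) and are handed it for a start the next day, so two or three non-starters in an arm is not shown to be likely. Safety reporting is descriptive (section 8.2.3), with no hypothesis or threshold. A fall from 20% to 18% is 0.4 of a subject in an arm of 20, and the exact 95% interval for 4/20 runs from about 6% to 44%. Counts in the AE table do not change; only percentages do. All of this stands, and it limits the point to a minor correction.

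**Non-starters would be visible anyway.** Section 8.2.2 lists treatment start and end dates for each premature discontinuation, and diaries and tablet counts record use. A careful reader could often rebuild the denominator. This stands in part: the listing covers only discontinuations, and the reported percentages would still rest on the wrong denominator.

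**An analysis plan may define the set more narrowly.** It may, and it was not available here. But the protocol is not silent: it states a rule, and a narrower set elsewhere would contradict it.

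**Counting everyone randomized is conservative.** That does not stand here. For an absolute AE proportion, subjects who cannot have an event can only lower it.

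**A stronger reading.** A reader might infer that the rule always understates the risk of humic acid. The documents do not support that for the comparison between arms, which step 4 shows moving in either direction. The downward effect is certain only for the proportion of an arm that has non-starters.

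**Conclusion.** The point holds as a minor one. Sections 7.1.1 and 7.1.4 tie AEs to exposure, section 8.2 does not tie the denominator to it, and the gap between randomization and first dose allows the two to differ. Each never-dosed subject in an arm of 20 lowers that arm's AE proportion by 5% in relative terms.

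This rests on reading section 7.1.1 literally and on using the section 8.2 set as the denominator of the AE table, since section 8.2.3 names no other. It is also conditional on at least one subject never dosing. The illustrative rates and non-starter counts are scenarios, not forecasts, and nothing in the protocol suggests that a conclusion of this descriptive pilot would change.

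**What to change.** Replace the sentence in section 8.2 with:

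> *The safety analysis will include all randomized subjects who took at least one dose of study product; subjects documented (diary, tablet count or subject report) as never having taken a dose will be excluded and listed separately, and subjects whose dosing cannot be determined will be retained.*

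The last clause is needed because a subject lost before Visit 2 may return neither diary nor tablets. Without a stated default, whether that subject belongs in the set would be decided after the fact.

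The cost is one sentence and no new procedure, since diaries and returned-tablet counts are already planned (sections 5.5, 6.1 and 6.4.3). The safety denominator becomes slightly smaller if there are non-starters, and a few subjects of unknown exposure may remain in it, so some dilution could persist. If everyone doses, the change has no effect.
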